7.2 Exclusion Criteria

Any subject who meets any of the following criteria will not qualify for entry into the study:

1. The subject has received any investigational compound within 30 days prior to Screening.
2. The subject has received TAK-491 in a previous clinical study or as a therapeutic agent.
3. The subject is an immediate family member, study site employee, or in a dependant relationship with a study site employee who is involved in the conduct of this study (eg, spouse, parent, child, sibling) or may consent under duress.

4. The subject has history of uncontrolled, clinically significant manifestations of metabolic (including diabetes mellitus, hypercholesterolemia, or dyslipidemia), endocrine, hematologic, pulmonary, cardiovascular, gastrointestinal, neurological, rheumatologic, skin and subcutaneous tissue disorders, infectious, hepatic, renal, urologic, immunologic, psychiatric or mood disorders (including any past history of suicide attempt), or a history of lactose intolerance, which may impact the ability of the subject to participate or potentially confound the study results.
5. The subject has a known hypersensitivity to any component of the formulation of TAK-491 or other AII inhibitors or related compounds.
6. The subject has a positive urine drug result for drugs of abuse or breath alcohol test at Screening or Check-in (Day -1).
7. The subject has a history of drug abuse (defined as any illicit drug use) or a history of alcohol abuse within 1 year prior to the Screening visit or is unwilling to agree to abstain from alcohol and drugs throughout the study.
8. Subject has taken any excluded medication, supplements, or food products listed in the Excluded Medications and Dietary Products table.
9. If female, the subject is pregnant or lactating or intending to become pregnant before, during, or within 30 days after participating in this study; or intending to donate ova during such time period.
10. Subject has current or recent (within 6 months) gastrointestinal disease that would be expected to influence the absorption of drugs (ie, a history of malabsorption, esophageal reflux, peptic ulcer disease, erosive esophagitis frequent [more than once per week] occurrence of heartburn, or any surgical intervention [eg, cholecystectomy]).
11. Subject has a history of cancer, except basal cell carcinoma that has been in remission for at least 5 years prior to Day 1.
12. Subject has positive test result for anti-HIV, anti-HCV antibodies, or for HBsAg at Screening.
13. Subject has used nicotine-containing products (including but not limited to cigarettes, pipes, cigars, chewing tobacco, nicotine patch or nicotine gum) within 28 days prior to Check-in (Day -1). Cotinine test is positive at Screening or Check-in (Day -1).
14. The subject has poor peripheral venous access.
15. Subject has donated or lost 450 mL or more of his or her blood volume (including plasmapheresis), or had a transfusion of any blood product within 30 days prior to Day 1.
16. Subject has a Screening or Check-in (Day -1) abnormal (clinically significant) ECG. Entry of any subject with an abnormal (not clinically significant) ECG must be approved, and documented by signature by the principal investigator.
17. Subject has abnormal Screening or Check-in (Day -1) laboratory values that suggest a clinically significant underlying disease or subject with the following laboratory

abnormalities: alanine aminotransferase (ALT) and/or aspartate aminotransferase (AST) $>1.5\times$ the upper limit of normal.

18. Subject has a hemoglobin value <12 g/dL at Screening.

19. The subject has a systolic blood pressure <110 and ≥160 mm Hg or a diastolic blood pressure <60 and ≥100 mm Hg at Screening or Check-in (Day -1).

7.3 Excluded Medications and Dietary Products

Use of the agents (prescription or nonprescription), foods, and supplements listed in [Table 7.a](#) is prohibited from the time points specified until completion of all study activities.

Table 7.a Prohibited Medications, Foods, and Supplements

28 days prior to Check-in (Day -1)	7 days prior to Check-in (Day -1)	72 hours prior to Check-in (Day -1)
Prescription medications	OTC medications (a)	Products containing caffeine or xanthine
Nicotine-containing products	Vitamin supplements	
Nutraceuticals (eg, St. John's wort, ginseng, kava kava, ginkgo biloba, Chinese herbs, and melatonin)	Foods or beverages containing grapefruit or grapefruit juice, star fruit or star fruit juice, Seville-type (sour) oranges and marmalade, apple, orange, or pineapple juice, vegetables from the mustard green family (eg, kale, broccoli, watercress, collard greens, kohlrabi, Brussels sprouts, mustard), and charbroiled meats	Poppy seeds
Immunization/Vaccines (b)		
Known OTC inhibitors/inducers of CYPs 3A4/5, 2C9, 2C19, 2D6, 1A2, 2B6, 2E1, and 2A6 (c)	Alcohol-containing products	

OTC=over-the-counter.

(a) Occasional use of acetaminophen (≤1 g/day) or other medication as approved by Takeda on a case-by-case basis is allowed except on Day 1.

(b) Inclusive of but not limited to flu vaccinations.

(c) Omeprazole, lansoprazole, cimetidine, ranitidine, and chlorpheniramine.

Subjects must be instructed not to take any medications, including over-the-counter medications, without first consulting with the investigator.

7.4 Diet, Fluid, and Activity Control, and Subject Housing

Subjects will be confined to the clinic from Day -1 through Day 11, and will return to the clinic for PK sampling on Days 12 to 13 and follow-up serum chemistry testing on Day 14.

During the confinement period, subjects will be given a menu consistent with local guideline and local dietary practice. Subjects will be given 3 meals and an evening snack every day, each containing approximately **20%** fat (relative to the total calories). The meals served on Day 1 and Day 10 should be identical between study days and for each subject in the study. The study menu

should be recorded and submitted to the study file with a copy provided to the sponsor prior to the start of the study.

If a blood draw or any study procedure coincides with a meal, the blood draw will take precedence followed by the study procedure and then the meal.

TAK-491 will be administered on Day 1 and Day 10 with 240 mL of water after a fast of at least 8 hours. On Day 1 and Day 10, subjects will also continue to fast for an additional 4 hours after dosing and subjects may consume water ad libitum with the exception of 1 hour before and 1 hour after drug administration. For Days 4 to 9, fasting is not required for dosing.

Subjects will remain upright (seated, standing, or ambulatory) for 1 hour following the dose administration, except as necessitated by the occurrence of an adverse event /or study procedures (eg, obtaining 12-lead ECG). Subjects will refrain from strenuous exercise throughout the entire course of the study.

7.5 Criteria for Discontinuation or Withdrawal of a Subject

The primary reason for discontinuation or withdrawal of the subject from the study should be recorded in the case report form (CRF) using the following categories. For screen failure subjects, refer to Section 9.1.14.

1. Pretreatment event (PTE) or adverse event (AE). The subject has experienced a PTE or AE that requires early termination because continued participation imposes an unacceptable risk to the subject's health or the subject is unwilling to continue because of the PTE or AE.
 - Liver Function Test Abnormalities
 - ALT or AST $>8 \times$ ULN, or
 - ALT or AST $>5 \times$ ULN and persists for more than 2 weeks, or
 - ALT or AST $>3 \times$ ULN in conjunction with elevated total bilirubin $>2 \times$ ULN or international normalized ratio (INR) >1.5 , or ALT or AST $>3 \times$ ULN with appearance of fatigue, nausea, vomiting, right upper quadrant pain or tenderness, fever, rash and/or eosinophilia ($>5\%$).
2. Significant protocol deviation. The discovery after administration of the first dose of study medication that the subject failed to meet protocol entry criteria or did not adhere to protocol requirements, and continued participation poses an unacceptable risk to the subject's health.
3. Lost to follow-up. The subject did not return to the clinic and attempts to contact the subject were unsuccessful. Attempts to contact the subject must be documented.

4. Voluntary withdrawal. The subject (or subject's legally acceptable representative) wishes to withdraw from the study. The reason for withdrawal, if provided, should be recorded in the CRF.

Note: All attempts should be made to determine the underlying reason for the withdrawal and, where possible, the primary underlying reason should be recorded (ie, withdrawal due to an AE should not be recorded in the "voluntary withdrawal" category).

5. Study termination. The sponsor, IRB, IEC, or regulatory agency terminates the study.

6. Pregnancy. The subject is found to be pregnant.

Note: If the subject is found to be pregnant, the subject must be withdrawn immediately. The procedure is described in Section [9.1.10](#).

7. Other.

Note: The specific reasons should be recorded in the "specify" field of the CRF.

7.6 Procedures for Discontinuation or Withdrawal of a Subject

The investigator may terminate a subject's study participation at any time during the study when the subject meets the study termination criteria described in Section [7.5](#). In addition, a subject may discontinue his or her participation without giving a reason at any time during the study. Should a subject's participation be discontinued, the primary criterion for termination must be recorded. In addition, efforts should be made to perform all procedures scheduled for the Study Exit Visit.

Discontinued or withdrawn subjects will not be replaced after the first dose of study drug.

8.0 CLINICAL TRIAL MATERIAL MANAGEMENT

This section contains information regarding all medication and materials provided directly by the sponsor, and/or sourced by other means, that are required by the study protocol, including important sections describing the management of clinical trial material.

8.1 Study Medication and Materials

A sufficient quantity of the following study drug for study conduct will be provided to the investigator.

- TAK-491 40 mg and matching placebo tablets.
- TAK-491 80 mg and matching placebo tablets.

8.1.1 Dosage Form, Manufacturing, Packaging, and Labeling

Dosage Form	TAK-491 40 mg and 80 mg white, round biconvex tablets and matching placebo. Tablets of the TAK-491 investigational drug for oral administration contain 40 mg or 80 mg of TAK-491F (the salt-free form of TAK-491) and will be provided in blister cards, matching placebo will also be provided in blister cards. The active formulation contains drug substance and excipients; placebo contains excipients only.
Manufacturing	Takeda Pharmaceutical Company Limited, Osaka, Japan.
Packaging	TAK-491 investigational medicinal product and matching placebo will be foil/foil blistered and packaged in 10-day (8 daily doses+2 extra doses) child-resistant blister cards. Each tablet is connected to a desiccant through a linked channel. Each blister card contains 10 TAK-491 tablets and 10 desiccants for the open-label part, and 20 TAK-491 or matching placebo tablets and 20 desiccants for the double-blind part. The tablets should not be removed from the blister card until immediately prior to dosing.
Labeling	Each blister card provided to the clinical site will be labeled with a single panel label with pertinent study information and appropriate country specific regulatory caution statement. Each label will include a space for the pharmacist to include a subject specific reference number. The blister cards will be labeled in an open labeled fashion for the open-label part and in a double-blind fashion for the double-blind part of the study.

8.1.2 Storage

TAK-491 investigational medicinal product and matching placebo should be stored at 25°C (77°F); with excursions permitted to 15°C to 30°C (59°F to 86°F). The blister cards in which the tablets are contained should not be opened until immediately prior to dosing in order to protect from moisture and humidity.

All investigational medicinal product must be kept in an appropriate, limited-access, secure place until it is used or returned to the sponsor or designee for destruction. All study medication must be stored under the conditions specified on the label, and remain in the original container until dispensed. A daily temperature log of the drug storage area must be maintained every working day.

8.1.3 Dose and Regimen

Table 8.a describes the dose and tablet count that will be provided to each group.

Table 8.a Study Medication Supplies

Treatment Description			
Regimen	Dose	Active	Placebo (a)
A	TAK-491 40 mg	One TAK-491 40 mg tablet	One placebo for TAK-491 80 mg tablet
B	TAK-491 80 mg	One TAK-491 80 mg tablet	One placebo for TAK-491 40 mg tablet
C (a)	TAK-491 placebo	Not applicable	One placebo for TAK-491 40 mg tablet One placebo for TAK-491 80 mg tablet

(a) Double-blind part of study only.

On Days 1 and 4 through 10, study drug will be administered. The investigator or investigator's designee will instruct the subject on dosing procedures.

Following administration of study drug, hand-and-mouth checks will be performed to ensure that the dose was swallowed and will be recorded on the source document. Although timing of events requires that each subject receive the appropriate dose at specific times, the exact dose time of consecutive subjects may be staggered to obviate the need to have all subjects on precisely the same study schedule. The actual date and time of administration of the dose of study drug will be recorded on the source documents and the appropriate CRF.

8.1.4 Overdose

An overdose is defined as a **known** deliberate or accidental administration of investigational drug, to or by a study subject, at a dose above that which is assigned to that individual subject according to the study protocol.

All cases of overdose (with or without associated adverse events) will be documented on an Overdose page of the CRF, in order to capture this important safety information consistently in the database. Adverse events associated with an overdose will be documented on AE CRF(s) according to Section 10.0, Pretreatment Events and Adverse Events.

Serious adverse events (SAEs) of overdose should be reported according to the procedure outlined in Section 10.2.2, Collection and Reporting of SAEs.

In the event of drug overdose, the subject should be treated symptomatically.

8.2 Study Medication Assignment and Dispensing Procedures

Subjects will be assigned, in the order in which they are randomized into the study to receive their treatment according to the randomization schedule allocated to the site. The Randomization Sequence Number will be entered onto the CRF.

Subjects will be assigned to receive a 4-digit randomization sequence number. The number will be assigned by the clinic site personnel in sequential order beginning with 1001 and ending with 1016 for the open-label part, and beginning with 2001 and ending with 2048 for the double-blind part.

This 4-digit number will be used by the clinical site to facilitate the prelabeling of pharmacokinetic samples, and will be the only subject identifier used on all sample collections. It should also be contained on the pharmacokinetic transport vials shipped to the bioanalytical laboratory, and will be used by the laboratory to report the subject data results. This 4-digit number should only be used for the purposes described in this section. It does not replace the 3-digit subject number which is assigned at the time the informed consent is obtained and which is used for all other procedures to identify the subjects throughout the study.

8.3 Randomization Code Creation and Storage

Randomization personnel of the sponsor or designee will generate the randomization schedule, which will be provided to the site pharmacist prior to the start of this study. All randomization information will be stored in a secured area, accessible only by authorized personnel.

8.4 Investigational Drug Blind Maintenance

For the double-blind part of the study, the investigational drug blind information is maintained through a randomization schedule held by the dispensing pharmacist.

8.5 Unblinding Procedure

For the double-blind part of the study, the investigational drug blind shall not be broken by the investigator unless information concerning the investigational drug is necessary for the medical treatment of the subject. All study assessments and causality should be performed, if possible, prior to unblinding. In the event of a medical emergency, if possible, the medical monitor should be contacted before the investigational drug blind is broken to discuss the need for unblinding.

For unblinding a subject, the investigational drug blind can be obtained by opening sealed envelope, or contacting the dispensing pharmacist.

The sponsor must be notified as soon as possible if the investigational drug blind is broken. The date, time, and reason the blind is broken must be recorded in the source documents and the same information (except the time) must be recorded on the (e)CRF.

If any site personnel are unblinded, investigational drug must be stopped immediately and the subject must be withdrawn from the study.

No change should be made to any assessment of the subject after unblinding.

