6.2 Justification for Study Design, Dose, and Endpoints

This randomized, open-label and double-blind, placebo-controlled, single- and multiple-dose, phase 1 study was designed with the following justification. The parameters listed as primary endpoints are considered appropriate for evaluation of pharmacokinetic profiles associated after single- and multiple-doses, and the additional safety endpoints comprise established safety assessments recognized as reliable, accurate, and relevant.

The pharmacokinetics of TAK-536 after administration of TAK-491 has been thoroughly characterized from data collected during the phase 1 clinical pharmacology program conducted in the United States and Europe. The $t_{1/2z}$ for TAK-536 following TAK-491 administration is approximately 11 hours; the planned sampling scheme after the single dose is approximately 6 half-lives and appropriate. Steady state of TAK-536 is achieved within 5 days of dosing of TAK-491; the multiple-dose duration is appropriate. A total of 64 healthy subjects will be enrolled into the study. An open-label design was used during the dosing of the first 16 subjects (in 2 consecutive cohorts) because the primary outcomes are based on objective measurements, that is, plasma concentrations of TAK-536. Fifteen of these first 16 subjects had a higher ALT and/or AST level on Day 11 than on Day -1. While none of these subjects had Day 11 ALT and/or AST values that exceeded 3×ULN of protocol mandated monitoring criteria (see [Section 7.5](#) [No.1] and [Section 10.2.3](#)), 7 of these exceeded the ULN. None of these ALT/AST elevations were accompanied by symptoms or signs of liver injury or by bilirubin elevation, and resolved without intervention. High frequency of subjects with elevations in ALT and/or AST levels were unexpected and unprecedented, as no similar findings were observed in previous TAK-491 phase 1 through 3 studies with the enrollment of subjects from different races and ethnicities (ie, Caucasians, African Americans, Mexican Americans, Native Americans, Asians, and other ethnicities). While other procedure-related factors, such as high-carbohydrate diet and minimal physical activity during the confinement period in the phase 1 unit, as described in the medical literature [\[10-12\]](#), might have been accountable for these asymptomatic ALT/AST elevations in the present study, a potential drug-related phenomenon has to be definitively ruled out. Hence, a

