11.0 STUDY-SPECIFIC COMMITTEES

No steering committee or clinical endpoint committee will be used in this study.

Takeda will designate an external hepatologist as an independent assessor of any liver enzyme elevation in the study. Takeda will also designate a Pharmacovigilance physician who is not involved in the study conduct as a sponsor liaison to participate and facilitate the safety communication between the external expert, the study site and Takeda.

All liver enzyme elevations occurring in the study subjects will be initially submitted to blinded review by the external hepatologist. The unblinded aggregate data from a series of patients will also be reviewed by the external hepatologist, a designated independent physician from the site, and a sponsor liaison before the next cohort is dosed with the support of an independent statistician, and a written assessment will be provided to Takeda liaison and the study PI in a real time.

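### Section 8.5 turns a code break into withdrawal from the study, so later scheduled PK samples and ALT/AST values are lost that could be collected without further dosing; its trigger also does not fit Sections 8.3 and 8.4

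*Protocol*

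**What the plan says.** Protocol Section 8.5 allows the investigator to break the blind only when the subject's medical treatment needs it. It names two sources for the code: "For unblinding a subject, the investigational drug blind can be obtained by opening sealed envelope, or contacting the dispensing pharmacist". It then sets the consequence: "If any site personnel are unblinded, investigational drug must be stopped immediately and the subject must be withdrawn from the study". No category of site staff is exempted.

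Two neighbouring sections place the code with a member of the site's staff. Section 8.3 describes a "randomization schedule, which will be provided to the site pharmacist prior to the start of this study", and Section 8.4 says that "the investigational drug blind information is maintained through a randomization schedule held by the dispensing pharmacist". Section 11.0 adds a liver review before each next cohort is dosed: "The unblinded aggregate data from a series of patients will also be reviewed by the external hepatologist, a designated independent physician from the site", together with a sponsor liaison.

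On what happens after withdrawal:

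- Section 7.6: "Discontinued or withdrawn subjects will not be replaced after the first dose of study drug". Efforts are made to carry out the Study Exit procedures.
- Section 9.3.11: the Early Termination visit includes clinical laboratory tests but lists no PK blood or urine. Appendix A, footnote (a), says not to take a PK sample at that visit unless one is due.
- Section 9.1.8: ALT/AST above the ULN on Day 11 and/or Day 14 is followed every 5 to 7 days until resolution, and values above 3×ULN are retested within 7 days.
- Section 10.2.1.2: adverse events are followed until they resolve or are explained.
- SAP Section 7.2: the safety set keeps non-completers. The PK set keeps anyone with at least one measurable concentration, and incomplete data are decided case by case.

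**The concern.** The rule joins two different things: ending treatment and ending participation. The second has a cost in data. Section 6.2 accepted an open-label first part "because the primary outcomes are based on objective measurements, that is, plasma concentrations of TAK-536", so by the protocol's own account a measured concentration does not become unreliable because someone knows the allocation. A measured ALT or AST value is a laboratory result of the same kind.

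The loss is also unlikely to be random. Because a code break requires a medical need, the subjects affected are likely to be those with a safety event. Section 6.2 says the placebo-controlled part was added because 15 of 16 open-label subjects had higher ALT and/or AST on Day 11 than on Day -1, and 7 exceeded the ULN. Ending scheduled liver chemistry in unblinded subjects thins the data where the question lies.

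Separately, a mandatory rule should say whose unblinding sets it off. As written, it covers all site staff, including a pharmacist who is unblinded throughout.

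**Working it through.** **1. The plan's own figures.** Sample size: 2 × 8 + 3 × 16 = 64, as stated. Section 13.3 says it does not rest on power, so there is no power calculation to reproduce. PK samples per subject (Table 9.d): 14 single-dose + 17 multiple-dose = 31. Single-dose sampling span (Section 6.2, half-life about 11 h): 72/11 = 6.5 half-lives, in line with the stated approximate 6.

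**2. Break between the Day 1 dose and the 72 h sample.** No dose is due in this window, so the remaining samples need no further drug. They are lost only because the subject is withdrawn. The Day 1 profile is predose plus 13 postdose times (0.5, 1, 2, 3, 4, 6, 8, 12, 16, 24, 36, 48, 72 h). As a rough guide I assume mono-exponential decline with an 11 h half-life, so the share of AUC still to come after time t is about 2^(−t/11).

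| Last sample taken | Samples lost of 14 | Half-lives covered | Approximate AUC share not observed |
|---|---|---|---|
| 12 h | 5 | 12/11 = 1.1 | 47% |
| 24 h | 3 | 24/11 = 2.2 | 22% |
| 48 h | 1 | 48/11 = 4.4 | 5% |
| 72 h (complete) | 0 | 72/11 = 6.5 | 1% |

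AUC-infinity and terminal half-life after the single dose are primary endpoints (SAP Section 5.1). With sampling ended at 24 h or earlier, both rest on little or no terminal-phase data. The later urine intervals, which feed the 72 h excretion parameters, go the same way.

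**3. Break before a scheduled chemistry panel.** Postdose panels are due on Day 4 (before dosing), Day 11 and Day 14.

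| Time of break | Scheduled panels lost | What remains |
|---|---|---|
| Before the Day 4 panel | Days 4, 11, 14 | One Early Termination panel |
| After the Day 4 panel, before Day 11 | Days 11, 14 | Day 4 and one Early Termination panel |
| Day 11 (after the panel) to Day 13 | Day 14 | Day 11, an Early Termination panel, and follow-up if Day 11 was above the ULN |

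The 5-to-7-day follow-up is tied to a Day 11 or Day 14 value. A subject withdrawn earlier may have neither. Adverse event follow-up helps only if the change is recorded as an event, which for laboratory values requires judged clinical significance (Section 10.1.3). No open-label subject exceeded 3×ULN on Day 11, so elevations of that size could fall outside both routes.

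**4. Size per case.** One subject is 1/16 = 6.25% of an arm. With the SD unchanged, a t-based 95% interval widens by the factor [t(0.975, n−1)/√n] / [t(0.975, 15)/√16]:

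- n = 15: (2.145/3.873)/(2.131/4) = 1.04
- n = 14: (2.160/3.742)/(2.131/4) = 1.08

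The SAP plans descriptive summaries only, so this is an illustration. Selective loss matters more than lost precision. SAP Section 7.11.2 tabulates shifts at each visit. If an arm had 7 of 16 above the ULN on Day 11 (the open-label proportion, 43.8%) and one of those seven had been withdrawn earlier, the Day 11 row would show 6/15 = 40.0%. With two, it would show 5/14 = 35.7%.

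**5. The trigger.** Section 8.3 gives the schedule to the site pharmacist before the study starts. Section 8.4 has the dispensing pharmacist hold it. Section 8.5 sends staff to that pharmacist for the code and then applies its consequence to all site staff without exception. These texts cannot all be followed word for word.

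**The case against.** Much of the case on the other side stands.

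- **Scope.** A reader might infer that all 48 double-blind subjects meet the trigger before dosing, because the pharmacist already has the code. Context does not support this. The rule closes a section about unblinding one subject, the same section relies on the pharmacist as a source of the code, and Section 8.4 describes the pharmacist's custody as the way the blind is kept. This is a wording defect, not a trial that cannot run.
- **Section 11.0.** A reader might also infer that each liver review sets off the rule. The site physician there is designated as independent and sees aggregate data; no disclosure of subject-level codes is described. The documents leave the point undefined, which is weaker than a contradiction.
- **Data already collected** are not discarded. Both analysis sets keep them, and Early Termination adds a chemistry panel.
- **Day 10 AUC24 and Cmax.** For a break before the Day 10 dose, these are lost because drug is stopped. Keeping the subject in the study would not recover a steady-state profile. Only a break in the 24 h after that dose, when no drug is left to stop, resembles the Day 1 case.
- **Day 10 samples at 36, 48 and 72 h** feed no parameter currently planned: Protocol Section 9.1.13 and SAP Table 7.c define the terminal-phase parameters for the single dose only, and SAP Table 7.a ends Day 10 sampling at 24 h.
- **Placebo arm.** Only 4 plasma samples per placebo subject are analyzed, and no urine. The PK loss therefore concerns the 32 subjects on active drug; the chemistry loss concerns all 48.
- **Bias.** It would be too strong to say that unblinding cannot bias the liver data. Clinical significance, recording as an adverse event, and causality are judgments.
- **Frequency.** The documents give no expected number of code breaks.

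What the objection does not answer is that no passage provides for the remaining single-dose samples or the scheduled Day 11 and Day 14 chemistry once the subject is withdrawn, although none of these needs a further dose.

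**Conclusion.** The point holds as a modest, inexpensive improvement. Section 8.5 ends later scheduled collection when a code is broken, and the loss that can be avoided is specific: single-dose samples up to 72 h after a break on Days 1 to 4, and scheduled ALT/AST values after a break before Day 11 or Day 14. Each case costs one unreplaced subject in an arm of 16, probably one with a safety event.

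The trigger wording is a clarification: 8.5 must be reconciled with 8.3 and 8.4, and should say how it relates to 11.0.

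The conclusion assumes that a withdrawn subject receives only the Early Termination procedures and the follow-up rules listed above, which is what the protocol provides for. The number of code breaks is unknown and likely low; with none, nothing is lost. The AUC shares rest on the mono-exponential approximation, and the Day 11 proportions on applying the open-label rate to one arm.

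**What to change.** In Section 8.5:

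1. Separate stopping of drug from withdrawal from the study. State that an unblinded subject, with consent, continues the already scheduled PK blood and urine collection for doses already given, the Day 4, Day 11 and Day 14 chemistry, and the follow-up call. The wording for the call already mentions the Early Termination Visit, so this only makes it explicit.
2. Flag these data as unblinded in the datasets and listings, with the day of the code break, so that summaries can be shown with and without them. Where dosing has ended early, the later ALT/AST values reflect a shorter exposure and should be read that way. Flag clinical significance and causality judged after unblinding as well.
3. Reconcile 8.5 with 8.3, 8.4 and 11.0 by stating whose unblinding triggers the rule and whether the aggregate liver review counts. Who triggers stopping of drug, and whether dosing stops, is for the sponsor to decide.

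The cost is two or three sentences and one flag variable. No visits or procedures are added to the existing schedule. The small downside is that some adverse event judgments will be made with knowledge of the allocation, which the flag makes visible.
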